**13.6 Withdrawal from Study Participation:**

Explain the process for withdrawal and specify whether or not the subjects will be given the opportunity to withdraw their data their data/specimens in the event they wish to withdraw from the study

Prior to the destruction of the link between participant name and research identification number (RIN; maintained and accessible only by the PI or designee in a password protected file stored on a secure server), participants will be able to withdraw their participation in the study by contacting the PI (or designee). Those who request to withdraw will be allowed to do so and their data will be removed from analysis for both this study and any future research for which the participant originally consented. After a link between a participant's name and her or his RIN has

been destroyed, we will no longer have the ability to identify the participant's data and, thus, she or he will no longer be able to have their data removed from the data set.

## 14.0

### Risks and Benefits

#### 14.1

##### Risks of Harm:

Identify all research-related risks of harm to which the subject will be exposed for each research procedure or intervention as a result of participation in this study. Consider the risks of breach of confidentiality, psychological, legal, social, and economic risks as well as physical risks. Do not describe risks from standard care procedures; only describe risks from procedures done for research purposes

Potential risks include: 1) breach of confidentiality, 2) coercion, and 3) discomfort and/or offense due to intervention content (i.e., sexual and reproductive health [SRH]). Risks associated with *breach of confidentiality* are always a consideration, but, these risks are considered low in this instance as all data will be identified by a research identification number (RIN). Risk of *coercion* is possible as military personnel may feel compelled to participate in the research study if they are informed about the study by their medical provider or someone in their chain of command. Risks associated with *feelings of discomfort* prompted by the content of the intervention are possible as the intervention and associated assessments concern SRH. However, content was developed in consultation with experts to ensure the information presented is focused on medically relevant and operationally focused concerns.

#### 14.2

##### Measures to Minimize Risks of Harm (Precautions, safeguards):

For each research procedure or intervention, describe all measures to minimize and/or eliminate risk of harms to subjects and study personnel

The potential risks (outlined above in "Risks of Harm") include: 1) breach of confidentiality, 2) coercion, and 3) discomfort and/or offense due to intervention content (i.e., sexual and reproductive health [SRH]).

*Protecting Confidentiality.* Every precaution will be taken to ensure data will be kept strictly confidential. During the informed consent process, potential participants will receive information about confidentiality, including who is able to view their data throughout the study. Data will be anonymous or identified by a research identification number (RIN); thus, the only way to identify whether or not an individual participated will be via documentation of informed consent. All electronic informed consent documents (ICDs) will be kept on a secure network. Only the PI and designees will have access to ICDs.

*Protection Against Coercion.* Protocols and research staff trainings related to ethics, confidentiality, and other topics in human subject protection will ensure participants are informed of their rights as a research volunteer. Throughout the recruitment process potential participants and others involved in the recruitment process by word of mouth will be told that participation is voluntary. During the informed consent process potential participants will be informed of their rights as a research volunteer, including the right to not participate in the research study without repercussions, to refuse to answer any question, to withdraw from the study at any time. Although supervisors/commanders may share information to participate in this study with service members, they will not be involved in group recruitment or consent. The majority of the consent process will be conducted by civilian members of our lab team.

*Protection Against Feelings of Discomfort.* Participants may feel uncomfortable by the intervention content (i.e., SRH) and associated assessment questions. The intervention was planned to attempt to minimize making participants feel uncomfortable. However, it is possible that some may still feel some discomfort by the topic nonetheless. Participants will be instructed during the consent process to contact the study team via telephone or email with any concerns

or to report discomfort. Participants will also be permitted to skip any questions in the assessments they do not feel comfortable answering.

**14.3****Confidentiality Protections (for research records, data and/or specimens):**

Describe in detail the plan to maintain confidentiality of the research data, specimens, and records throughout the study and at its conclusion (e.g., destruction, long term storage, or banking). Explain the plan for securing the data (e.g., use of passwords, encryption, secure servers, firewalls, and other appropriate methods). If data will be shared electronically with other team members/collaborators outside the institution, describe the method of transmission and safeguards to maintain confidentiality. Explain whether this study may collect information that State or Federal law requires to be reported to other officials or ethically requires action, e.g., child or spouse abuse

As described in the section above ("Measures to Minimize Risks of Harm"), confidentiality protections include:

- Collecting data only identified by a research identification number (RIN)
- Using the informed consent process as an opportunity to inform potential participants about their rights as a research participant and to provide transparency in plans for data management.

**14.4****Potential Benefits:**

Describe any real and potential benefits of the research to the subject and any potential benefits to a specific community or society

If the individuals in the research are considered experimental subjects (per 10 USC 980), and they cannot provide their own consent, the protocol must describe the intent to directly benefit all subjects

Potential benefits to the participant include an increased knowledge in sexual and reproductive health (SRH) information, self-efficacy related to reducing health-risking sexual behaviors (HRSBs), and decrease HRSBs. The intervention has the potential to significantly benefit the overall health and readiness of military personnel, as SRH issues such as sexually transmitted infections (STIs) and unplanned pregnancy degrade mission readiness.

**14.5****Privacy for Subjects:**

Describe the measures to protect subject's privacy during recruitment, the consent process, and all research activities, etc.

In accordance with HIPAA policies at the Uniformed Services University of the Health Sciences (USU) and The Miriam Hospital (TMH), and despite data only being used for study purposes, participants' data will be treated in a manner similar to protected health information to afford it equivalent privacy protections. Recruitment will most be via word of mouth and advertisement online and on paper, so there are no privacy risks associated with this type of recruitment. Consent will be done electronically in a HIPAA-compliant software.

**14.6****Incidental or Unexpected Findings:**

Describe the plan to address incidental findings and unexpected findings about individuals from screening to the end of the subject's participation in the research. In cases where the subject could possibly benefit medically or otherwise from the information, state whether or not the results of screening, research participation, research tests, etc., will be shared with subjects or their primary care provider. State whether the researcher is obligated or mandated to report results to appropriate military or civilian authorities and explain the potential impact on the subject

Incidental findings are not anticipated as the app is not collecting personal health information.

## 15.0 Study Monitoring

### 15.1 Your study requires either Data and Safety Monitoring Plan (DSMP) or a Data and Safety Monitoring Board (DSMB).

- DSMP
- DSMB
- Both
- Not Applicable

A DSMP should describe the plan to monitor the data to verify that the data are collected and analyzed as specified in the protocol. Include who will conduct the monitoring, what will be monitored, and the frequency of monitoring. It should also include the plan to ensure the safety of subjects

The Principal Investigator (PI) or designee(s) will verify that all data has been collected and analyzed as specified. The project coordinator (or designee to be appointed by the PI) is responsible for reporting findings to the PI on a weekly basis. Deviations from the protocol will be reported to the PI within 24 hours of discovery by the research team so that a determination of notification to the Institutional Review Board (IRB) and any mitigation procedures can be implemented in a timely manner.

It is possible that participants may feel discomfort answering questions or consuming information related to sexual and reproductive health (SRH), despite the benefits that come from gaining knowledge about SRH. Participants will be encouraged to contact the research study or their healthcare providers if they experience distress. All research study members will be trained to refer participants to their healthcare providers.

## 16.0 Reportable Events

### 16.1 Reportable Events: Consult with the research office at your institution to ensure requirements are met. Describe plans for reporting unexpected adverse events and unanticipated problems. Address how unexpected adverse events will be identified, who will report, how often adverse events and unanticipated problems will be reviewed to determine if any changes to the protocol or consent form are needed and the scale that will be used to grade the severity of the adverse event.

Consult with the research office at your institution to ensure requirements are met

- Describe plans for reporting expected adverse events. Identify what the expected adverse events will be for this study, describe the likelihood (frequency, severity, reversibility, short-term management and any long-term implications of each expected event)
- Describe plans for reporting unexpected adverse events and unanticipated problems. Address how unexpected adverse events will be identified, who will report, how often adverse events and unanticipated problems will be reviewed to determine if any changes to the research protocol or consent form are needed and the scale that will be used to grade the severity of the adverse event

No adverse events are anticipated. It may be possible that a participant may experience embarrassment, discomfort, or offense due to the subject matter of the intervention. If participants contact the research team reporting such feelings, the research team will be trained to refer them to appropriate services such as those for psychological and/or medical care if they have further concerns. Such feelings that cause greater than minimal interference with usual social and functional activities will be considered an adverse event. The PI will report any unanticipated adverse events to the Institutional Review Board (IRB) within 72 hours of discovery. When reporting the unanticipated adverse event to the IRB the PI will propose any amendments to the research protocol if applicable and as necessary.

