The SRH Knowledge Pre-Test Assessment will be administered to participants in the application at the onset of the intervention. The SRH Knowledge Pre-Test will assess baseline SRH knowledge that will be used to tailor select content in the app to the participant (see Study Procedures for more information and examples).

The Participant Post-Test Assessment will be administered to participants after completion of the intervention via an online data collection software (e.g., REDCap, SurveyMonkey). All questions in the Participant Post-Test Assessment must be answered. However, a participant may respond that she or he "Prefer Not to Answer" for any question. The Participant Post-Test Assessment assess sexual and reproductive health (SRH) knowledge, attitudes, self-efficacy, and acceptability of the intervention.

Data will also be collected on participants' interactions with the app. This data includes information such as information on how long participants spent on each component, how many times participants opened the app, and how many times participants accessed and completed components.

Participants who consent to opt-in to an additional structured, qualitative interview will be asked to complete an interview with a member of the USU team via telephone two-to-six weeks after receiving the intervention. The interview will ask participants about their experiences using the app, including-but-not-limited-to questions about graphics (aesthetics), barriers to use, and ease of use (see attached interview agenda). Interviews will be recorded, and recordings will be used to expand notes taken during the interview. Recordings will be deleted upon completion of interview notes.

**10.3 At any point in the study, will you request, use, or access health information in any form, including verbal, hard copy and electronic?**

Yes  No

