**13.3 Please describe the pre-screening process. If no pre-screening, enter Not Applicable in the text editor**

Participant eligibility in the overall study will be determined by anonymous self-reported responses to screening questions including age and active duty military status. Participants will be invited to complete an interview based on their answers to demographic questions in the de-identified Pre-Intervention Assessment and whether or not they used the app (pulled from de-identified app analytics data). Medical records from the Military Health System (MHS) will not be utilized at any point during the study, and will not be used to identify subjects or confirm eligibility.

**13.4 Consent Process: Revised Common Rule, Section 219.116: General requirements for informed consent, whether written or oral, are set forth in this paragraph and apply to consent obtained in accordance with the requirements set forth in paragraphs (b) through (d) of this section. Broad consent may be obtained in lieu of informed consent obtained in accordance with paragraphs (b) and (c) of this section only with respect to the storage, maintenance, and secondary research uses of identifiable private information and identifiable biospecimens.**

Are you requesting a waiver or alteration of informed consent?

Yes  No

Please explain the consent process:

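### Section 16.1 adverse events come to light only if a participant gets in touch, and no listed post-intervention domain measures them, so a low count cannot be read as absence of harm

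*Combined protocol and SAP*

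**What the plan says.** All references are to the combined protocol and SAP.

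- **Definition.** Section 16.1 states "No adverse events are anticipated", allows that the subject matter may embarrass or upset someone, and then sets a threshold: "Such feelings that cause greater than minimal interference with usual social and functional activities will be considered an adverse event".
- **Detection.** The action in 16.1 is conditional: "If participants contact the research team reporting such feelings". Section 14.2 describes the same route: "Participants will be instructed during the consent process to contact the study team via telephone or email with any concerns". Section 15.1 adds an alternative: "Participants will be encouraged to contact the research study or their healthcare providers if they experience distress".
- **Other sources.** Section 13.3 rules one out: "Medical records from the Military Health System (MHS) will not be utilized at any point during the study".
- **Survey content.** Section 10.2 says of the survey after the intervention: "The Participant Post-Test Assessment assess sexual and reproductive health (SRH) knowledge, attitudes, self-efficacy, and acceptability of the intervention". It lists general mental health for the pre-intervention survey only. Item-level content is in an attached Measures document.
- **Interviews.** Sections 10.2 and 11.5 plan about 40 telephone interviews on experience with the app. The topic list is expressly open.
- **Use in decisions.** The optimization criteria in 9.3 are improvement in outcomes within 25 minutes of content. Section 11.1 plans factorial analysis of variance of component effects. Neither mentions a harm measure.

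**The concern.** The definition turns on how far the feelings interfere with daily life, which only the participant can report. The plan describes no occasion on which participants are asked. A participant who is upset and does nothing, or who speaks to a provider, leaves no trace in the trial's data. The form's own prompt for 16.1 asks how unexpected adverse events will be identified; the answer gives a threshold and waits for contact.

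Two things are at stake. First, a final report of few or no adverse events would mix the true rate with the willingness to call or email a research team about a sensitive subject, and the two could not be separated. Second, the trial exists to choose components. Some of them, such as narrative videos with negative outcomes and a simulation of the user's own risk of infection or unplanned pregnancy, could plausibly cause distress. Participants are randomised to have each component on or off, but as written nothing on harm is collected systematically to compare.

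The other two risks named in 14.1, coercion and breach of confidentiality, are in a similar position: 14.2 describes prevention, and no domain listed in 10.2 checks whether either occurred.

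**Working it through.** **Inputs from the plan.** 720 evaluable, 20% attrition and 900 enrolled (11.5); five on/off components giving 32 conditions (10.1). The plan states no adverse event rate and no rate of contact, so every event rate and capture fraction below is an assumption.

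**The plan's own figure.** 720 / (1 − 0.20) = 900, which reproduces exactly. Each component therefore compares about 450 on with 450 off among those enrolled, and 360 with 360 among completers.

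**What a zero count would mean.** The one-sided 95% upper limit p solves (1 − p)^n = 0.05, so p = 1 − 0.05^(1/n). If only a fraction c of events is reported, the compatible true rate is p / c.

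- Contact by participants is open to everyone enrolled, so n = 900: 1 − 0.05^(1/900) = 0.33%.
- At 10% capture: 0.33% / 0.10 = about 3.3%.
- At 25% capture: 0.33% / 0.25 = about 1.3%.
- If all 720 completers were asked and none reported an event: 1 − 0.05^(1/720) = 0.42%.

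**What counts to expect under the present method.** With true rate r and capture c, the expected count is 900 × r × c and the chance of no report is (1 − r × c)^900.

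- r = 1%, c = 5%: 0.45 expected; chance of zero 64%.
- r = 2%, c = 10%: 1.8 expected; chance of zero 17%.
- r = 5%, c = 10%: 4.5 expected; chance of zero 1%.
- r = 5%, c = 25%: 11.25 expected; chance of zero below 0.1%.
- With full capture, true rates of 1%, 2% and 5% would give 9, 18 and 45 events.

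The count could be under 1 or over 10. Its relation to the true number is unknown.

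**What a comparison by component could show.** Two-sided 5% test of two proportions, normal approximation: power = Φ[(|p1 − p0| − 1.96 × SE0) / SE1], where SE0 uses the pooled rate and SE1 the separate rates. For 5% versus 10% with 360 per level, SE0 = √(2 × 0.075 × 0.925 / 360) = 0.0196 and SE1 = √((0.0475 + 0.0900) / 360) = 0.0195. Power = Φ[(0.05 − 0.0385) / 0.0195] = 72%.

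- All completers asked, 360 versus 360: 72% for 5% versus 10%; 35% for 2% versus 4%; 20% for 1% versus 2%.
- Contact only at 10% capture, 450 versus 450: about 14%, 8% and 6% for the same true rates. These are rough at such small counts.

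Asking everyone makes the counts interpretable. It does not give a well-powered harm comparison unless events are fairly common.

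**The case against.** The case on the other side has real force.

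- **A reader might infer that the plan guarantees a count close to zero.** The documents do not support that. They give no event rate and no contact rate, and the range above runs from below 1 to more than 10. What they show is under-ascertainment of unknown size.
- **A reader might infer that no instrument asks about distress, pressure or confidentiality.** That cannot be confirmed. The Measures document and interview agenda are attachments not available here, the interview topics are open, and acceptability could cover discomfort or offence. What stands is that no listed domain names these matters and no section sends such answers to adverse event review.
- **A reader might see 16.1 as contradicting 14.1, 14.2 and 15.1, because discomfort is foreseen while no adverse event is anticipated.** It does not. Those sections foresee discomfort, offence or distress; 16.1 reserves the term adverse event for feelings that interfere with functioning. An event at that level can be read as unanticipated and so reportable to the IRB.
- **A reader might infer that the weekly report to the PI in 15.1 has nothing to act on.** The text does not describe that report as a feed of adverse events, so this does not follow.
- **Safeguards exist.** Participants are told at consent how to raise concerns, and may decline to answer questions. This is proper, but it is not a means of counting events.
- **A harm criterion is partly a matter of preference.** The stated criteria are outcome improvement and length, and the power figures show the limits of any comparison. That argues for a descriptive table, not against asking the question.

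**Conclusion.** The concern holds in a limited form. As written, an event meeting the 16.1 definition is detected only through contact by the participant, with no described return route from a provider and no listed post-intervention domain that measures it. A low or zero count would therefore say little about harm: zero reports from 900 is compatible with 0.33% at full capture, about 1.3% at 25% and about 3.3% at 10%. The capture fractions are assumptions; the direction of the error is not. The plan also provides no harm information by component at the point of selection.

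This does not threaten the efficacy analysis. It is an inexpensive improvement to safety ascertainment that is worth making. It falls away in part if the Measures document already contains a suitable item, in which case only the routing and the table are missing.

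**What to change.** 1. Unless the Measures document already has one, add to the Post-Intervention Assessment a fixed item on distress, embarrassment or offence from the app, with the 16.1 interference wording as its response scale. Add short items on pressure to take part and on breach of confidentiality, both named in 14.1. If such items exist, cite them in 16.1.
2. State that positive answers go to the PI for classification under 16.1.
3. Add to 11.1 one table of the distress item, on versus off for each component, labelled descriptive, to be read alongside the selection outcomes. Make no formal test or claim of no difference.
4. Optionally, clarify in 16.1 that any event meeting the definition is reported to the IRB, whether or not the underlying discomfort was foreseen.

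The cost is an amendment, one table and about a minute in a survey of 20 to 30 minutes that is already sent to participants around two weeks after they are asked to complete the app. It needs no extra visit, staff or sample size. There will be more events to review. Survey non-completers, 900 − 720 = 180 under the plan's attrition assumption, would still be missed, and they may include distressed participants. The contact route should therefore stay in place beside the new items.
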